We will use semi-structured interviews to examine dyadic experiences with the MSM Intervention. Qualitative data will be analyzed by the PIs using the conventional content analysis approach. This approach is used to describe a phenomenon where existing theory or research literature is limited. Data from the tape-recorded interviews will be transcribed and analyzed using HyperRESEARCHTM qualitative software. Transcripts will be imported allowing for the development of analytic categories, data coding, and review of coded data. All data will be read repeatedly to achieve immersion and obtain a sense of the whole. Then, data will be read word by word to derive codes. Codes will then be sorted into themes based on links and relationships. Separate investigators with experience in qualitative data analysis ([name] and [name]) will conduct a final validation review of the codes and themes to ensure consistency and clarity across all qualitative data. Data discordantly coded will be discussed for refinement and consensus purposes.

Geriatric Assessment (GA) data for both FCGs and patients will be analyzed descriptively. We will use descriptive statistics (mean [SD], median [range], percentage [95% confidence interval]) to summarize GA scores and domains. We will also describe the patterns of changes in GA over time for both FCGs and patients. Changes will be calculated as post-surgery scores minus pre-surgery scores. Exploratory logistic regression models (univariate and multivariate) will be fitted to study the correlation between GA and FCG/patient outcomes.

COVID-19 qualitative data will be analyzed using content analysis approaches as described under exploratory aim 2.

Social determinants of health (SDH) data will be scored according to guidelines descriptively summarized. We will use multiple linear regression to test associations between baseline outcomes and SDH predictors. Baseline scores of outcomes activation, burden preparedness, self-efficacy, QOL and distress will be summarized with descriptive statistics. Distributions of SDH predictors will be summarized. For each outcome, we will use bivariate regression to assess the effect of one predictor at a time. Stepwise multivariate analysis will be performed to select all significant predictors (p<0.05). In addition, multicollinearity issues will be examined by calculating correlation matrix for all predictors and by checking variance inflation factors.

Spiritual well-being data will be scored according to guidelines and descriptively summarized. Two subscale scores of spiritual well-being outcomes will be measured before (baseline) and after surgery (3-months post-discharge). Pre and post-surgery data will be compared to assess potential changes in each subscale scores for patient and FCG arms separately. We will use Generalized Estimation Equations (GEE) for comparison, adjusting for sociodemographic covariates. Similar to multiple regression analyses for research questions 1.1 and 1.2, both bivariate and multivariate GEE models will be performed. Multicollinearity will also be examined.

IRB 17238 02/02/2023

Key Informant/Focus Group Data Analysis

A codebook will be co-developed by the principal investigators of the parent R01 and the diversity supplement, along with study participants. Grounded Theory methods of emerging coding will be used and facilitated by QDA Miner. To ensure data validity, constant comparison method—each theme and interpretation will be compared with emerging findings from data analysis— will be used to confirm emerging themes. Member checking techniques—results will be returned to participants for accuracy and resonance of experiences— will be utilized to validate focus group results.

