FCG Activation in Transitions Tool (FCAT) – This 10-item survey was designed to assess FCG's level of engagement and preparedness to care for patients during care transitions. Psychometric assessment was conducted in two randomly equivalent waves of participants

IRB 17238 02/02/2023

(N=434), including FCGs of patients with cancer and/or chronic lung disease. The estimated person-separation reliability was 0.84. 111

Patient Activation Measure (PAM) – This measure assesses patient "activation", which uses a Guttman-like scale that reflects a patient's level of engagement and empowerment in their healthcare. ¹¹² Cronbach's alpha from our pilot study was 0.92.

Self-Efficacy Scale - This tool is a modified version of the Self-Efficacy Scale developed by Lorig and colleagues. ¹¹³ It contains 8 items that assesses FCG's and patient's perceived confidence in self-management. Items are rated on a 4-point Likert scale, and higher scores represent higher confidence. Cronbach's alpha from our pilot study was 0.89.

Surgery-Related Knowledge Tool - This tool was developed by the investigators to assess FCG and patient post-operative recovery knowledge. Each item addresses specific content within the MSM intervention to assess changes in knowledge. Scoring is based on the number of questions answered correctly.

Exploratory:

Society of Thoracic Surgeons General Thoracic Surgery Database Data Collection Form – This form will be used to record clinical and surgical characteristics. These include date of diagnosis, pre-operative risk factors, pre-operative treatments, pre-operative pulmonary function tests, date of surgery, type of surgical procedures, admission date and status, clinical staging, postoperative events/complications, discharge date and status, discharge disposition, pathological staging, and smoking cessation plans.

Exit Interview Discussion Guide – Qualitative data will be obtained through semi-structured interviews using a discussion guide. The guide contains a series of overarching questions, presented in an open-ended fashion. The questions are designed to solicit FCGs' and patients' experiences with participating in the intervention. FCGs and patients will be interviewed separately.

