13.0 Statistical Considerations

13.1Study Design

Our target sample size for this study will be 200 caregiver-patient dyads (after 20% attrition). The planned sample size is 100 caregiver-patient dyads per treatment group. The power of statistical tests (two-sided 0.05 level of significance) is shown below for the primary outcomes of each specific aim. The effect sizes are shown as pairs of numbers representing the expected control group mean, based on published data, and the hypothetical population mean for the intervention care group. The SD column is based on published data, and power is conservatively estimated for a simple t-test on a single post-intervention measurement. The planned analysis, described in section E.5, will adjust for baseline values, and will combine longitudinal assessments, both of which will improve power.

A total of 80 new cases of stage I-III surgically treated NSCLC were available at City of Hope in fiscal year 2015. Our institutional race distribution is 56.2% Caucasian, 20.5% Hispanic, 4.7% Black, 13.5% Asian, and 5.1% other (38.7% ethnic minorities overall). These statistics should reflect the anticipated race distribution for participants. All efforts will be made to accrue minorities. Our pilot study demonstrates that we are able to accrue minorities (38%) to match the population at City of Hope.

A sample size of 100 per arm was calculated, based primarily on outcome means and variation observed in our previous studies (see Section E.1 for sample size calculations and power analysis). We have projected attrition based on previous studies. We will enroll 100 participants per arm to allow for 20% drop-out/attrition during the course of the study. We will enroll a total of 200 dyads in order to retain 160 dyads at 3-months. With a 52 month accrual plan, we estimate that 4 caregiver-patient dyads will need to be accrued per month. With a total pool of 80 potential dyads per year, this yields approximately 7 dyads per month that are eligible for the study. Hence, we will have a sufficient pool of eligible participants for study accrual. In our lung cancer Program Project (N=366), we were able to enroll 4 FCGs and patients per month. ^{59, 114}

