with 83% power. Caregiver burden is described by the research team's previous work¹¹⁴ with mean objective burden subscale scores of near 22.0, with a pooled standard deviation of 4.0. With 80 subjects per group, a reduction by 1.8 points could be detected with 81% power. **Hypotheses 1.2** address preparedness for caregiving and QOL. In our previous work, preparedness has been reported on a 1 to 5 scale with a mean of approximately 3.7 and SD of 0.72. An increase in mean score from 3.7 to 4.1 could be detected with 93% power. Total QOL scores for 157 FCGs are reported by our previous work¹¹⁴, with a mean total score of 5.93 and a standard deviation of 1.42. An increase in mean total QOL score of 0.7 could be detected with 87% power. **Hypothesis 1.3** address changes in FCG cancer support services use. Here, we will classify each FCG as to whether they had an encounter with social work services and family resource center. A difference of 20 percentage points for social work referrals and 30 percentage points for family resource center would be detectable with 80 subjects per group.

Specific Aim 2 addresses the effects of the MSM Intervention on patient outcomes, and **Table 4** provides patient outcome effect size and power. **Hypothesis 2.1** addresses patients' psychological distress and QOL, and **Hypothesis 2.2** addresses healthcare resource use. For each

Table 4. Patient Outcomes Effect Size and Power

Outcome	Measure	Detectable effect	SD	Power
H2.1 Psychological distress	Distress thermometer	3.5 v 2.4	2.4	82%
H2.1 QOL	FACT-L	93.7 v 101.3	17.0	80%
H2.2 Resource use	Any use (y/n)	53% v 31%	NA	80%

of these outcomes, the mean control group value, the root mean square (RMS) standard deviation, and the detectable improvements (Delta) in mean score was calculated

for a two-sided 0.05 significance level test using 80 subjects per group. For resource use, we will classify each patient as to whether they had in-home nursing care, urgent care/ER visits, or a readmission. In preliminary data, 20 of 38 subjects had such an event, indicating that a difference of 22 percentage point would be detectable with 80 subjects per group.

Specific Aim 3 addresses the effect of outcome mediators on FCG and patient outcomes

Table 5. Outcome Mediator Effect Size and Power

Outcome	Measure	Detectable effect	SD	Power
H3.1 Activation	PAM and FCAT	72.0 v 80.0	18.0	80%
H3.1 Self-Efficacy	Self-Efficacy Tool	20.0 v 22.0	22.0	80%
H3.1 Knowledge	Knowledge Tool	8.5 v 9.0	1.0	88%

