
(Table 5). Standard deviations (SD) were estimated from previous data. For activation, an improvement of the mean by 8.0 points could be detected with 80% power. For self-efficacy, an improvement of 2.0 points could be detected

IRB 17238 Packet: 26 with 80% power. For knowledge, a difference of 5.0 points can be detected with 88% for 80 dyads per group.

Sample Size and Power Calculation for Social Determinants of Health and Spiritual Well Being – Sample size calculation is based on linear multiple regression method using

G*power (Version 3.1.9.4). This method tests the null hypothesis that the proportion of variance of the outcome explained by a set of predictors is zero (i.e., $R^2=0$), while the alternative hypothesis is $R^2>0$. Significance level is 0.05 and power is 0.8. 20% of attrition was considered in calculation.

Two parameters need to be specified for sample size calculation⁷⁴: effect size and number of predictors. The effect size is the ratio of proportion of variance explained by a set of predictors and error variance⁷⁴. Since there is no published data for correlation between our outcomes and predictors in the target population (lung cancer), and due to the exploratory nature of the analyses, the effect sizes are estimates only. To cover

Effect size Number of predictors 0.15 0.25 0.35 137 87 65 14 162 104 80 19 184 119 92

132

102

203

24

Table 2. Sample size considering 20% attrition

potential effect sizes that our data may reveal, we employed different levels of effect size defined by Cohen⁷⁵: small 0.15, medium 0.25, and large 0.35. The total number of predictors is 24 for FCG arm and 23 for patient arm. However, some predictors come from the same SDH domain, thus they would be highly correlated. To avoid multicollinearity in multiple regression model, some predictors may be removed from the final model. Therefore, we also used different number of predictors to calculate sample size (**Table 2**). Assuming the effect size 0.35 and 20% attrition, our target sample size will be 51 dyads (102 total participants) to detect deviation of R² from zero with 0.05 significance level and 80% power.

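### Table 5 claims 80% power for self-efficacy, but its printed inputs (20.0 v 22.0, SD 22.0) give about 9%; the text also gives the knowledge effect as 5.0 points where the table has 0.5

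*Combined protocol and SAP*

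**What the plan says.** Section 13.1 sets the rules for all the power tables. On the level and scope it says: "The power of statistical tests (two-sided 0.05 level of significance) is shown below for the primary outcomes of each specific aim". On the test it says that "power is conservatively estimated for a simple t-test on a single post-intervention measurement". On numbers it says: "We will enroll a total of 200 dyads in order to retain 160 dyads at 3-months", which is 80 per group, and the Aim 3 text also works with 80 dyads per group.

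For Aim 3, the self-efficacy row of Table 5 reads "20.0 v 22.0 22.0 80" (the last figure is a percentage): control mean 20.0, intervention mean 22.0, SD 22.0, power 80%. The text below the table agrees on the effect: "For self-efficacy, an improvement of 2.0 points could be detected", with 80% power.

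For knowledge, Table 5 has 8.5 against 9.0, SD 1.0, power 88%. The text says: "For knowledge, a difference of 5.0 points can be detected with 88% for 80 dyads per group".

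The instrument is described in section 12.1.3 (Self-Efficacy Scale). It has 8 items, is completed by both caregivers and patients, and is rated as follows: "Items are rated on a 4-point Likert scale, and higher scores represent higher confidence". No scoring rule is given.

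**The concern.** A 2-point difference against an SD of 22 is a standardised effect of 0.09. The other continuous rows in the power tables have standardised effects of 0.44 to 0.56 and stated powers of 80% to 93%. An effect about one fifth of that size cannot have 80% power at the same sample size. The SD also looks wrong in itself, since it is nearly as wide as the full range of an 8-item, 4-point sum score and equals the mean in the neighbouring cell.

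Self-efficacy is one of the three mediators named in the central hypothesis (section 1.0). It is tested directly in Hypothesis 3.1, and the synopsis lists it among the outcome mediators under the primary endpoints. If its 80% power is not real, a null result in caregivers or patients could be read as evidence that the intervention does not work through self-efficacy, when the comparison may have had little chance of showing it. In the knowledge sentence, an effect ten times too large appears beside a power that belongs to a different effect.

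**Working it through.** **Inputs.** Two-sided alpha 0.05, simple two-sample t-test, n = 80 per group (section 13.1); means, SDs and stated powers from Tables 3 to 5.

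**Formula.** Noncentrality λ = (difference / SD) × √(n/2), with √(80/2) = 6.325. Degrees of freedom are 2 × 80 − 2 = 158 and the critical value is 1.975. Power is the probability that a noncentral t variable with parameter λ falls outside ±1.975.

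**Step 1: does this method reproduce the plan's other figures?**

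| Row | Difference / SD | λ | Computed | Stated |
|---|---|---|---|---|
| Caregiver distress | 1.2 / 2.6 | 2.92 | 82.7% | 83% |
| Caregiver burden | 1.8 / 4.0 | 2.85 | 80.8% | 81% |
| Preparedness | 0.4 / 0.72 | 3.51 | 93.7% | 93% |
| Caregiver QOL | 0.7 / 1.42 | 3.12 | 87.3% | 87% |
| Patient distress | 1.1 / 2.4 | 2.90 | 82.2% | 82% |
| FACT-L | 7.6 / 17.0 | 2.83 | 80.2% | 80% |
| Activation | 8.0 / 18.0 | 2.81 | 79.8% | 80% |
| Knowledge (Table 5) | 0.5 / 1.0 | 3.16 | 88.2% | 88% |

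All eight agree within 1 percentage point, so the method is the one the plan used.

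**Step 2: self-efficacy as printed.** 2.0 / 22.0 = 0.091 and λ = 0.575. Power is 8.8%, against 80% stated.

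**Step 3: can another reading rescue it?** With the printed difference and SD:
- one-sided 0.05: 14%
- 100 per group, no attrition: 9.8%
- 160 per group, caregivers and patients pooled as if independent: 12.8%
- baseline adjustment with an assumed correlation of 0.9 (not in the documents), so SD = 22 × √(1 − 0.81) = 9.59: 26%

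None comes near 80%. Holding SD at 22.0, 80% power needs about 1,900 per group for 2.0 points, or a difference of 9.8 points with 80 per group.

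**Step 4: is SD 22.0 possible?** Means of 20 and 22 cannot be item means on a 4-point scale, so the score is most naturally a sum. Eight items with a width of 3 each give a range of 8 × 3 = 24 (8 to 32, or 0 to 24). The largest SD on a bounded range is half its width, 24 / 2 = 12, reached only with half the sample at each end. With 0-to-24 scoring and a mean of 20, the bound is √((24 − 20) × (20 − 0)) = 8.9. So 22.0 is impossible for a sum score.

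**Step 5: what would power be at possible SDs?** Difference 2.0, 80 per group. The SDs are assumed values, since the documents give no other:

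| SD | 4 | 4.5 | 5 | 6 | 12 |
|---|---|---|---|---|---|
| Power | 88% | 80% | 71% | 55% | 18% |

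The SD that gives exactly 80% is 4.49.

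**Step 6: the knowledge sentence.** A difference of 0.5 with SD 1.0 gives 88.2%, as the table says. A difference of 5.0 with SD 1.0 gives essentially 100%. The 88% therefore belongs to 0.5.

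**The case against.** The strongest reply is that this is one mistyped cell and the comparison itself is adequately powered. Table 5 lists detectable effects. An SD of 4.5 would give 2 / 4.5 = 0.444, the same standardised effect as the activation row (8 / 18 = 0.444) and the same 79.8% power. On that reading the 2.0 points and the 80%, which the table and the text both state, are right and only the SD is wrong. The 8.8%, the 1,900 per group and the 9.8 points would then show only that the row is inconsistent, and would not describe the trial. This is plausible and may be what happened. But the documents do not contain 4.5, and a reader cannot recover the true SD from them: at SD 5 or 6 the power would be 71% or 55%.

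A second reply is that section 12.1.3 gives no scoring rule, so a rescaled score (0 to 100, say) could have an SD of 22. That stands as a limit on the word impossible. It does not help the power claim, because with SD 22.0 the power is 8.8% on any scale.

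A third reply is that little depends on this row. Nothing shows that it determined the 100 dyads per arm, and the continuous rows for Aims 1 and 2 reproduce at 80 per group. Mediation will be judged by structural equation modelling, and section E.5 promises confidence intervals that do not use the planning SD. This is correct and limits the consequence to the Aim 3 power statement. That statement is still wrong as written. The knowledge error is a decimal slip in the text; the table is right.

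**Conclusion.** The concern holds. As printed, the self-efficacy row supports 8.8% power, not 80%, and it is the only continuous row in Tables 3 to 5 that does not reproduce. The SD of 22.0 exceeds the maximum of 12 for a sum score. That bound assumes sum scoring, which the means of 20 and 22 point to but the plan does not state. The power result needs no such assumption.

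The actual power for a 2-point difference cannot be determined from the documents. It is near 80% if the SD is about 4.5, and falls to 55% at SD 6 and to 18% at the bound of 12. The knowledge effect in the text is ten times the value in Table 5, and the table's 0.5 is the one consistent with 88%. The sample size for the trial is not put in question.

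**What to change.** 1. Find the self-efficacy SD in the data from which the planning values were taken. The pilot used this scale (section 12.1.3 reports its Cronbach's alpha as 0.89), so an observed SD should exist. With only 22 caregivers in the pilot, an SD for caregivers alone will be imprecise, and its uncertainty should be stated.
2. Replace 22.0 in Table 5 with that SD, recompute by the same t-test with 80 per group, and report the resulting power for 2.0 points or the difference detectable with 80% power. Giving caregivers and patients separately would be useful because both complete the scale, but it is optional.
3. State the scoring rule (sum, mean or rescaled) in section 12.1.3, so that means and SD can be checked against the range.
4. In the Aim 3 text, change the knowledge difference from 5.0 to 0.5 points.

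The cost is a protocol wording change. The stated power for self-efficacy may turn out lower than 80%. Enrolment, procedures and the planned analyses stay as they are.

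### The sample-size table for the social determinants and spiritual well-being studies allows for 20% attrition by multiplying by 1.2, so its target of 102 keeps too few for 80% power after that loss

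*Combined protocol and SAP*

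**What the plan says.** The calculation is in section 13.1, in the paragraphs on sample size and power for social determinants of health and spiritual well-being. It uses the G*Power routine for linear multiple regression: "This method tests the null hypothesis that the proportion of variance of the outcome explained by a set of predictors is zero". The settings are given as "Significance level is 0.05 and power is 0.8", and the text adds that "20% of attrition was considered in calculation".

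The effect size is defined so: "The effect size is the ratio of proportion of variance explained by a set of predictors and error variance". That is Cohen's f². Three levels are used: "small 0.15, medium 0.25, and large 0.35". On predictors: "The total number of predictors is 24 for FCG arm and 23 for patient arm". The text adds that some may be dropped because of multicollinearity.

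The accompanying table (the second one numbered 2 in the protocol) is titled as already allowing for 20% attrition. Its legible rows, for f² of 0.15, 0.25 and 0.35, are:
- 14 predictors: 162, 104, 80
- 19 predictors: 184, 119, 92
- 24 predictors: 203, 132, 102

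A further row, 137, 87, 65, has lost its predictor count in the available text. The conclusion drawn is: "Assuming the effect size 0.35 and 20% attrition, our target sample size will be 51 dyads (102 total participants"). The inflation formula is not stated.

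Earlier in the same section the main trial says what 20% attrition means: "We will enroll a total of 200 dyads in order to retain 160 dyads at 3-months".

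**The concern.** There are two common ways to allow for 20% loss, and only one does what is intended. If 20% of those enrolled are lost, the number to enrol is N/0.8 = 1.25N. Multiplying by 1.2 keeps only 1.2 × 0.8 = 0.96 of N, which is 4% too few before rounding.

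The main trial works on the first basis, with 200 enrolled, 160 retained, and Tables 3 and 4 powered on 80 per group. If the add-on table uses the second, one section applies the same attrition rate in two ways, and the 80% power stated for the add-on target does not survive the loss that it claims to cover. What is at stake is the accuracy of a quoted sample size and power. The main trial's enrolment is not affected.

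**Working it through.** **Inputs, all from section 13.1.** F test of R² = 0, significance level 0.05, power 0.80, f² = 0.15, 0.25 or 0.35, k predictors, 20% attrition. Retention in the main trial is 160/200 = 0.8.

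**Formula.** For N analysed observations, df1 = k, df2 = N − k − 1, and noncentrality λ = f² × N. Power is the probability that a noncentral F exceeds the upper 5% point of the central F. The required N is the smallest that gives power of at least 0.80.

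**Reproducing the plan's table.** In each cell the values run in the order f² = 0.15 / 0.25 / 0.35.

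| k | Required N | N × 1.2, rounded up | Plan | N/0.8, rounded up |
|---|---|---|---|---|
| 14 | 135 / 86 / 66 | 162 / 104 / 80 | 162 / 104 / 80 | 169 / 108 / 83 |
| 19 | 153 / 99 / 76 | 184 / 119 / 92 | 184 / 119 / 92 | 192 / 124 / 95 |
| 24 | 169 / 110 / 85 | 203 / 132 / 102 | 203 / 132 / 102 | 212 / 138 / 107 |

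The 1.2 multiplier matches all nine labelled cells exactly, and N/0.8 matches none. The gaps are 7/4/3, 8/5/3 and 9/6/5 participants.

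**The row without a label.** With k = 9 the required N is 114/72/54. Times 1.2, rounded up, this is 137/87/65, as printed; N/0.8 would be 143/90/68. With k = 8 the required N is 109/69/52, and N/0.8 rounded up is also 137/87/65. The row alone therefore cannot show which formula was used. The step of five between 14, 19 and 24 points to 9.

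**The target cell (k = 24, f² = 0.35).**
- Required N = 85 (power 80.7% at 85, 79.9% at 84).
- Plan: 85 × 1.2 = 102.
- Retained after 20% loss: 102 × 0.8 = 81.6, so 81 or 82.
- Power: 77.2% at 81, 78.2% at 82.
- Correct inflation: 85/0.8 = 106.25, so 107. In whole dyads this is 54 dyads, or 108 participants. 108 × 0.8 = 86.4, and power at 86 is 81.5%.

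Across the nine labelled cells, power at the retained number is about 77% to 79%.

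**Without attrition.** At 102 analysed, k = 24 and f² = 0.35, power is 91.1%.

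**Separate regressions for caregivers and patients.** At 51 analysed and f² = 0.35, power is 39.1% with 24 predictors (caregivers) and 41.2% with 23 (patients), before any loss.

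**The case against.** Several points on the other side have force.

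- **Attrition may not touch the SDH analysis.** The study calendar has the SDH questionnaire at baseline only, and the analysis text regresses baseline outcomes on SDH predictors. Loss by 3 months does not remove those data, and 102 would give about 91% power. This stands. A reader might infer that the SDH analysis misses 80% power outright; the documents do not support that. The shortfall applies to the calculation as stated, which claims to cover 20% loss.
- **The spiritual well-being analysis is a different analysis.** It compares baseline with 3 months by GEE, and the measure's description says caregivers do not complete the survey. A 102-person R² test does not describe it. This stands too: 77% to 78% is the power of the stated calculation, and has not been shown to be the power of any planned analysis.
- **Not every cell is proven.** It is tempting to say that the whole table has the error. The unlabelled row fits the 1.2 multiplier with 9 predictors and N/0.8 with 8, so only nine cells are established.
- **Fewer predictors may be kept.** With 22 predictors, power at 81 or 82 is 80.3% or 81.2%. That is true, but the target was taken from the 24-predictor row.
- **The main trial's wording is not clean.** Section 13.1 also calls 200 dyads the target after 20% attrition. The sentence on enrolling 200 to retain 160, and the 80 per group in Tables 3 and 4, still settle the meaning.
- **The slip is small beside the uncertainty in effect size.** Agreed. The plan calls the effect sizes estimates only and the analyses exploratory. That limits the importance, but it does not make the attrition step right.

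**Conclusion.** The concern holds in a limited form. The nine labelled cells, including the headline 102, use N × 1.2 where the protocol's own meaning of attrition requires N/0.8. The unlabelled row very probably does the same, if its count is 9. At the target, 20% loss leaves 81 or 82 of the 85 needed, and power is about 77% to 78%, not 80%. The target is 5 participants short, or 6 once rounded to whole dyads.

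This rests on the fixed-model F test with λ = f² × N, on all 24 predictors being kept at f² = 0.35, on attrition applying, and on one regression that pools caregivers and patients. The last assumption matters most. The text gives predictor counts separately for caregivers and patients but counts 102 as 51 of each. A reader might take 107 or 108 as confirming the design; it does not. If the two groups are analysed separately with all predictors, correcting the inflation alone leaves power far below 80%.

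The error is minor, and it touches only an exploratory add-on.

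**What to change.** 1. Recompute the table as N/0.8, rounded up: 14 predictors 169/108/83; 19 predictors 192/124/95; 24 predictors 212/138/107. If the first row is for 9 predictors, it becomes 143/90/68.
2. Either restate the pooled target as 54 dyads (108 participants), or keep 51 dyads and state about 77% to 78% power after 20% loss.
3. State that the attrition step does not apply to the baseline-only SDH regressions, for which 85 are required and 102 give about 91% power.
4. State that all these figures assume one regression pooling caregivers and patients, and do not hold if each is analysed separately (about 39% to 41% power at 51 each with all predictors).

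The cost is one table and a few sentences. If 51 dyads are kept, nothing in the conduct of the study changes; moving to 54 adds three dyads to the add-on, within the 200 that the main trial plans to enrol.
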